- Treatment arm 3: LPV/r 800 mg-200 mg orally twice on Day 1, followed by 400 mg-100 mg orally twice daily for an additional 9 days (Days 2 to 10)
- Treatment arm 4: Ascorbic acid 1 gm orally twice on Day 1, followed by 500 mg orally twice daily for 9 days (Days 2 to 10)

Objectives and Endpoints:

Objectives	Endpoints
Primary	

 • To test the efficacy of LPV/r compared to placebo to resolve COVID-19 symptoms within 14 days. 	
 • COVID-19 symptoms are based on the following criteria: 
 ○ At least TWO of the following symptoms: Fever ($\geq 38^{\circ}\text{C}$), chills, rigors, myalgia, headache, sore throat, new olfactory and taste disorder(s), OR ○ At least ONE of the following symptoms: cough, shortness of breath or difficulty breathing, OR ○ Severe respiratory illness with at least 1 of the following: 
 ▪ Clinical or radiological evidence of pneumonia, OR ▪ Acute respiratory distress syndrome (ARDS), OR ▪ LRTI, defined by resting $\text{SpO}_2 < 93\%$ sustained for 2 readings 2 hours apart AND presence of subjective dyspnea or cough 
Death or COVID-19-related hospitalizations will count as a failure to resolve symptoms.

 • To test the efficacy of LPV/r compared to placebo to reduce SARS-CoV-2 viral shedding 	
 • Time to clearance of nasal SARS-CoV-2, defined as 2 consecutive negative swabs (swabs collected daily Day 1 through Day 14) 
Trial is statistically powered for this endpoint in both the high- and lower-risk populations, analyzed separately.

Secondary	

 • To test the safety of LPV/r compared to placebo for treatment of high-risk outpatients with SARS-CoV-2 infection 	
 • Serious adverse events (including death and COVID-19-related hospitalization) and adverse events resulting in treatment discontinuation

 To test whether LPV/r has an effect on disease severity compared to placebo 	
 Peak score on WHO Ordinal Scale for Clinical Improvement Peak score on modified Flu-PRO within the first 14 days

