
 To test whether LPV/r is associated with decreased viral shedding from self-collected nasal swabs over 14 days compared to placebo 	
 Proportion of days with SARS-CoV-2 detected from mid-nasal swabs by PCR Median quantity of SARS-CoV-2 detected from mid-nasal swabs by PCR
Exploratory	

 To assess pharmacokinetics and exposure-response relationship of LPV/r 	
 LPV/r blood concentration in DBS

COVID-19: coronavirus disease; DBS: dried blood spot; Flu-PRO: inFLUenza patient-reported outcome; LPV/r: lopinavir-ritonavir; LRTI: lower respiratory tract infection; SARS-CoV-2: severe acute respiratory syndrome coronavirus 2; SpO2: blood oxygen saturation level; WHO: World Health Organization.
	

Sample Size:

The study will enroll 173 participants per arm to achieve 80% statistical power at 2-sided type I error rate of 5% for a pairwise comparison against the control to detect a treatment effect of hazard ratio of 1.5 for the primary outcome(s) assuming control event rate of 60% for the primary outcome and 5% dropout rate. Additional controls will be added to allow for contemporaneous controls for the LPV/r arm. Eligible participants will be randomized at a 1:1 ratio LPV/r + and Ascorbic acid. If a second eligible patient is in the same household, both will be assigned to the same regimen. A blinded sample size re-assessment may be done to possibly increase the target sample size, conditional on the observed incidence rate and within household correlation. Should a new intervention be added, the randomization ratio may be adjusted to favor the new arm, ensuring that control arm participants are still enrolled concurrently with active arms; an empirical Bayesian information borrowing method may be used to incorporate past control arm data for the comparison of new intervention that is added later.

Duration:

Twenty-eight days of clinical follow-up per participant.

Proposed Sites (up to 6): University of Washington, Tulane, Boston University, Cook County, and others to be discussed

2. Schedule of Activities

Procedure	Screening	Self-quarantine									EOS	
		Treatment Period										
	Day 0 ^a	Day 1 ^a	Day 2 ^a	Day 3	Day 4 ^a	Days 5 to 8	Day 9 ^a	Days 10 to 13	Day 14 ^a	Day 21	Day 28 ^b	
Informed consent	X											
Demography	X											
Sign HIPAA form	X											

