It is anticipated that additional treatment modalities will be incorporated into this protocol, in an adaptive fashion. Those will be added through later protocol amendments, which will define additional sample size needs and any potential change to randomization (e.g., changing the randomization ratio, continuation/discontinuation of any of the existing arms, etc.).

Participants will be counseled about the preliminary *in vitro* data on and LPV/r activity against SARS-CoV-2 and equipoise regarding efficacy in humans, given that there are only limited data from an uncontrolled study at this time.

Participants may participate in a sub-study where they will be asked to provide a dried blood spot (DBS) sample for therapy concentration and pharmacokinetics of the medications as well as for SARS-CoV-2 antibody testing.

An independent data and safety monitoring board (DSMB) will be convened for this study with expertise in COVID-19 or respiratory viruses and emerging epidemics as well as biostatistics. The purpose of the DSMB is to monitor the study for operational futility, social harms, and efficacy. The DSMB will also review the blinded sample size re-assessment plan and proposed

sample size changes and make recommendations on the randomization ratio, in case the new intervention arms are added.

This multi-center study will be conducted in high COVID-19 disease incidence areas in the United States, with the potential to expand enrollment to international sites.

5.2. *Participant and Study Completion*

Up to 173 high and low-risk participants per arm will be randomly assigned to study treatment or control. This sample size target may increase based on the blinded sample size re-assessment.

A participant is considered to have completed the study if he/she has completed all phases of the study, including the last scheduled procedure shown in the Schedule of Activities (SoA).

This study will be considered completed when sufficient number of participants complete the study to enable appropriate evaluation of the primary endpoint.

6. Study Population

Prospective approval of protocol deviations to recruitment and enrollment criteria, also known as protocol waivers or exemptions, is not permitted.

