11.1. Sample Size Determination

The overall size of the study is driven by the clinical endpoint, resolution of COVID-19 symptoms.

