11.1.1. COVID-19 Endpoints

Overall sample size will depend on the number of events observed. To detect at least a 1.5-fold increased risk of the COVID-19 symptom resolution rate under a null hypothesis of no reduction

and four interim monitoring analyses with stopping for futility and efficacy based on the O'Brien-Fleming bounds and 80% power, the trial is designed to achieve 99 events per pairwise comparison for the symptom resolution endpoints. To achieve this, 173 participants will be enrolled per arm.

As the initial sample size target, 210 per arm was chosen for each experimental group (HCQ, HCQ + azithromycin), assuming a control arm rate of approximately 30% and 5% dropout rate.

HR (active/control)	Events/arm	N per arm	Median control arm (days)	Median active arm (days)*
1.4	142	247	10	7
1.5	99	173	10	7
1.6	75	129	10	6
1.7	59	103	10	6
1.8	49	85	10	6
1.9	41	71	10	5
2,0	36	63	10	5

*Under constant baseline hazard assumption

11.1.2. *Viral Shedding Endpoint*

Assuming the median time to cessation of viral shedding is 10 days and a constant baseline hazard for cessation of shedding, approximately 62% of participants would no longer experience viral shedding at 14 days under the null hypothesis of no intervention effect. Assuming 420 participants per pairwise comparison, 90% statistical power, 1-sided type I error rate of 2.5% for efficacy, we can detect at least a 37% increase in the rate of cessation of viral shedding. Under an extreme example of having only half that sample, 210, we could detect an increase of 54% or higher.

11.2. *Populations for Analyses*

For analysis purposes, the following populations are defined and will be described in greater detail in the trial Statistical Analysis Plan:

Population	Description
Intention to Treat (ITT)	All enrolled participants
Modified ITT	All enrolled participants who do not have LRTI at Baseline: high-risk group for the primary clinical endpoint; high- and low-risk groups (separately) for the primary virologic endpoint.
PK evaluable	Participants from the DBS sub-study with at least 1 interpretable PK sample.

DBS: dried blood spot; PK: pharmacokinetic; PCR: polymerase chain reaction; SARS-CoV-2: severe acute respiratory syndrome coronavirus 2.

11.3. *Statistical Analyses*

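### Section 11.1.2 claims 90% power for 37% and 54% faster viral clearance, but its own 62% assumption gives about 76% and 74%; the sample sizes are obsolete and the by-cohort power claim has no support

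*Protocol*

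**What the plan says.** Time to viral clearance by Day 14 is one of the two primary endpoints. Protocol section 11.1.2 assumes a 10-day median with constant hazard, so that "approximately 62% of participants would no longer experience viral shedding at 14 days under the null hypothesis of no intervention effect". With 420 participants per pairwise comparison, 90% power and a one-sided 2.5% error rate, it concludes that "we can detect at least a 37% increase in the rate of cessation of viral shedding". It then adds: "Under an extreme example of having only half that sample, 210, we could detect an increase of 54% or higher".

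Section 11.1.1 shows where these sizes come from: "210 per arm was chosen for each experimental group (HCQ, HCQ + azithromycin"). Section 5.1 says those two regimens were stopped and LPV/r was added. For the current comparison, section 5.2 says: "Up to 173 high and low-risk participants per arm will be randomly assigned to study treatment or control".

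On the risk cohorts, the synopsis table of objectives says of this endpoint: "Trial is statistically powered for this endpoint in both the high- and lower-risk populations, analyzed separately". The synopsis sample-size paragraph gives 80% power at hazard ratio 1.5 for the primary outcomes, with 5% dropout. SAP section 1.5.2, written for the hydroxychloroquine arms, claims power for this endpoint only in the two cohorts combined: a 60% increase with 200 clearance events.

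**The concern.** Power for a time-to-event comparison depends on the number of events. If 62% of controls clear within the window, 420 participants cannot supply the events that 90% power at hazard ratio 1.37 requires. The 210-participant statement would need more events than it has participants.

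The text also describes a design that no longer exists, and it leaves the current 346 participants without a specific power statement for this endpoint. Section 11.3.1 runs the primary analyses overall and by cohort. A reader who trusts the synopsis could therefore take a null result in one cohort as evidence of no effect, when power there was low.

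**Working it through.** **Inputs.** From section 11.1.2: control median 10 days, constant hazard, one-sided 2.5% (z = 1.960), 90% power (z = 1.282). From section 4: a 14-day swab window. From section 7.5: 1:1 allocation. From the synopsis: 5% dropout, hazard ratio (HR) 1.5, 80% power (z = 0.842).

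**Reproducing the clearance figure.** Control clearance by Day 14 is p0 = 1 − 0.5^(14/10) = 0.621. This matches the stated 62%.

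**Formulas.**
- Active-arm clearance: p1 = 1 − (1 − p0)^HR
- Expected events: D = N(1 − dropout)(p0 + p1)/2
- Power: Φ(½·√D·ln HR − 1.960)
- Events needed: 4(1.960 + z_power)²/(ln HR)²

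**The two stated claims, no dropout.**

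| N | HR | p1 | Events D | Power | Events needed for 90% | Detectable increase at 90% |
|---|---|---|---|---|---|---|
| 420 | 1.37 | 0.735 | 285 | 75.7% | 424 | 46% (stated 37%) |
| 210 | 1.54 | 0.776 | 147 | 74.4% | 225 | 70% (stated 54%) |

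For the first row, ½ × √284.9 × ln 1.37 = 2.657, and Φ(2.657 − 1.960) = 75.7%.

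This reading favours the plan, because the active arm is allowed to clear faster. With 62% clearance in both arms, power is 72% and 69%. A log-rank simulation with daily visits gave 76% and 73%.

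**Likely source of the stated figures.** If 420 participants are treated as 420 events, the detectable HR at 90% power is exp(2 × 3.242/√420) = 1.372, which is the stated 37%. The same slip with 210 gives 1.564, near the stated 1.54 but not equal to it. Freedman's formula, a two-proportion test, one-sided 5%, a 28-day window and reading N as per arm did not reproduce the pair of figures.

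**Check of the method.** SAP 1.5.2 has 200 events at 90% power: exp(2 × 3.242/√200) = 1.58, consistent with its stated 60%.

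**Current design, N = 346, 5% dropout.**
- At HR 1.5: p1 = 0.767, D = 346 × 0.95 × (0.621 + 0.767)/2 = 228, power about 86%.
- At HR 1.37: power about 65%.
- Detectable increase: 53% at 90% power and 45% at 80%.
- Four O'Brien-Fleming interim looks plus the final (efficacy bounds, equal spacing) need about 3% more events. The detectable increases become 54% and 46%, and power at HR 1.5 becomes 85%.
- The documents give no household design effect. An assumed range of 1.05 to 1.20 on top of the interim looks gives 56–61%, 47–51% and 84–79%.

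**By cohort at HR 1.5, 5% dropout.** Events needed for 80% power are 4(1.960 + 0.842)²/(ln 1.5)² = 191. Participants needed are 191/[0.95 × (0.621 + 0.767)/2] ≈ 290 per cohort, or 580 for both, against 346. Whatever the split, the smaller cohort has at most 346/2 = 173. That yields 114 events and 58% power (60% with no dropout).

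**The case against.** The strongest reply is that little depends on this text. Section 11.1 says: "The overall size of the study is driven by the clinical endpoint, resolution of COVID-19 symptoms". No enrolment number comes from 11.1.2, and the combined analysis exceeds the 80% target at HR 1.5. The separate-cohort sentence appears only in the synopsis table; the matching row in section 4 omits it. All of this stands, and it limits the severity.

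A second reply is that the synopsis sentence gives no effect size or power level, and that blinded sample-size re-assessment or borrowing of earlier placebo data could raise power. The 58% ceiling does assume HR 1.5, 346 participants and no borrowing. But HR 1.5 is the protocol's own target for its primary outcomes, and both remedies are conditional and unquantified. They cannot support a present-tense claim of adequate power.

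Third, the restated figures are approximate. Clearance is dated to the first of two negatives in SAP 4.1.3, so the last possible event is Day 13. That lowers control clearance to 59.4% and moves the detectable increases to 55% and 46%. The 3% interim inflation covers efficacy bounds only; one assumed futility rule raises it to about 7%. In addition, section 11.1.1 attaches the four looks to the symptom endpoint, while section 5.1 leaves interim analysis to a later decision. Each of these shifts moves the result by only one or two percentage points.

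**Conclusion.** The concern holds. On the section's own assumptions the claimed 90% power is about 76% at 420 participants and 74% at 210. The correct detectable increases at 90% power are about 46% and 70%. The sizes belong to the stopped arms. For the current 346 participants with 5% dropout, the figures are about 53% at 90% power and 45% at 80%, before interim looks and clustering. These results rest on exponential clearance times, a 14-day window and 1:1 allocation.

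The claim of power within each cohort has no calculation or enrolment quota behind it. At HR 1.5 with 346 participants it fails for at least one cohort under any split. The error should be corrected, but it does not make the combined comparison underpowered for the protocol's target effect.

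**What to change.** In section 11.1.2, delete the sentences on 420 and 210 participants and restate for 173 per arm, for example:

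> With about 62% control clearance by Day 14 and 5% dropout, the trial has 90% power to detect an increase of about 53% (80% power: about 45%) in the clearance rate in the combined cohorts, before allowance for interim analyses and household clustering. Four O'Brien-Fleming interim looks raise these to about 54% and 46%, and household clustering raises them further.

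If the interim plan for this endpoint differs, or includes futility stopping, recompute the second sentence to match.

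In the synopsis table, delete the sentence on separate power, or replace it with:

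> The trial is not separately powered for this endpoint within each risk cohort.

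The by-cohort analyses in sections 11.2 and 11.3.1 can stay as they are. The cost is wording in two places and a less favourable stated detectable effect. No enrolment number, analysis or endpoint status changes.

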5.1. Overall Design

The overarching goal of this study is to assess the effectiveness of interventions on the symptom duration, and length of viral shedding among adult outpatients with SARS-CoV-2 infection to inform public health control strategies.

This is a randomized, multi-center, placebo-equivalent (ascorbic acid +/- folic acid)-controlled, blinded platform trial. Stratified randomization based on different trial sites will be used. The trial started with HCQ (Intervention A) and HCQ + azithromycin (Intervention B) to assess the efficacy on the prevention of LRTI progression. With this protocol amendment, HCQ and HCQ/azithromycin were stopped, and LPV/r (Intervention C) was added. The trial may allow for additional agents to be added and tested against placebo with standardized eligibility criteria, outcomes, and measurements.

This study will enroll 173 eligible adults per arm (18 to 80 years of age) with high risk for disease progression or at low risk at baseline who are PCR-confirmed SARS-CoV-2 infection with symptoms compatible with COVID-19. Eligible participants will be enrolled and randomized in a 1:1 ratio to LPV/r or Vitamin C. Recruitment rate will be assessed on a weekly basis starting at the end of second week after the first eligible patient is recruited and randomized. Blinded sample size re-assessment will be done to increase the sample size target, should a lower control event rate (CER) and/or higher dropout rate than expected be observed. A decision for a possible interim analysis will be made during the trial based on the information on the observed recruitment rate, the CER, the dropout rate, and the final sample size target, if applicable. The decision for interim analysis will be made in a blinded manner (e.g., based on pooled number of events). The interim monitoring plan (written by the Study Statistician) will define monitoring bounds to maintain the 2-sided type I error rate at the desired 5% (e.g., 97.5% or higher probability of superiority over the control group). Should new experimental candidates be added during the trial, randomization ratios may be adapted to favor the new arms.

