The Statistical Analysis Plan will be developed and finalized before database lock and will describe the participant populations to be included in the analyses, the detailed analytical plans with endpoints and procedures for accounting for missing, unused, and spurious data. An Interim Monitoring Plan will also be developed to describe approaches for re-estimation of sample size and any planned interim analyses. This section presents a brief summary of the planned statistical analyses of the primary and secondary endpoints (these are listed in [Section 4](#)).

11.3.1. *Efficacy Analyses*

Demographic characteristics (age, sex, race) of each study group will be tabulated.

The mean age (plus range and standard deviation) by sex of the enrolled participants, as a whole and per group, will be calculated.

Primary analyses: The primary analyses will be conducted on the intend-to-treat population overall and by cohort (high-risk and low-risk). Participants randomized to each active treatment will be compared to participants randomized to placebo (ascorbic acid). If appropriate, the primary analysis will make use of all participants randomized to placebo, whether contemporaneously enrolled or not, using an Empirical Bayesian information borrowing method (described below). Due to anticipated heterogeneity in risk of disease progression, pre-specified baseline variables, including age, BMI, and days of symptoms at time of enrollment will be included in the model to increase precision.

Both primary endpoints will be analyzed using a Cox proportional hazards model with robust standard errors, adjusted for within household correlation.

As-treated analysis: The primary analyses will be repeated, replacing randomization arm by actual treatment to account for possible off-label use of and noncompliance to the investigational products.

Subgroup analyses: All subgroup analyses will be pre-specified in the Statistical Analysis Plan. Any further subgroup analyses will be considered ad hoc.

Missing Data

Due to the design of the study and retention activities, measurable outcomes are expected for all participants. However, in the unlikely event of a missing test result, the missing data will be imputed.

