2. GENERAL DATA ANALYSIS CONSIDERATIONS

Descriptive statistics that will be used to summarize continuous variables are as follows: mean and standard deviation, median and interquartile range, quartiles, range, and number of missing data values. If applicable, continuous data that are skewed will be transformed to meet assumptions of normality. For categorical variables, descriptive statistics that will be used include the following: frequencies, relative frequencies, and the number of missing data values. Descriptive analyses summarizing baseline and follow-up data will be stratified by site and/or country. Line, scatter and box plots will be used, as appropriate, for longitudinal data representations. An alpha level of 0.05 will be used for all statistical tests unless otherwise specified.

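### The protocol gives no rule for controlling error across two primary endpoints and three analysis populations; if any one success counts, a false primary finding has a chance of about 7–22%, depending on which tests are confirmatory

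*Protocol*

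**What the plan says.** **Endpoints.** The protocol Synopsis and section 4 list two primary endpoints: resolution of COVID-19 symptoms within 14 days and time to clearance of nasal virus. Section 11.3.1 states: "Both primary endpoints will be analyzed using a Cox proportional hazards model with robust standard errors".

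**Populations.** Three places differ.
- Section 11.3.1, under primary analyses: "The primary analyses will be conducted on the intend-to-treat population overall and by cohort (high-risk and low-risk"). Subgroup analyses have their own paragraph in the same section.
- The modified ITT row in section 11.2 uses only the high-risk group for the clinical endpoint, and the two risk groups separately for the virologic endpoint.
- The endpoint table in the Synopsis claims power for viral clearance in each risk population on its own. The matching table in section 4 does not carry that sentence.

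**Alpha.** The Synopsis gives "80% statistical power at 2-sided type I error rate of 5% for a pairwise comparison against the control", for a "hazard ratio of 1.5 for the primary outcome(s) assuming control event rate of 60% for the primary outcome and 5% dropout rate". Section 11.1.2 uses 1-sided 2.5% for viral shedding, again without a split. The only mechanism for protecting the error rate is in section 5.1, where interim monitoring bounds are "to maintain the 2-sided type I error rate at the desired 5" percent.

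**Decision rule.** None is stated. Section 3 calls the viral endpoint co-primary once, in a list of participant tasks.

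**SAP.** Section 1 limits the SAP to the first three arms. Symptom resolution is secondary there (sections 1.2 and 7.3), and shedding is tested with the risk cohorts combined (section 4.1.3). Section 2 adds a general default: "An alpha level of 0.05 will be used for all statistical tests unless otherwise specified". Lopinavir-ritonavir appears only in the section 4.1.2 objective, with no data set attached.

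**The concern.** Two endpoints in three populations make up to six tests that section 11.3.1 places under primary analyses. Each endpoint carries the full alpha, and nothing ranks one above another. A result with p<0.05 in one cohort for one endpoint could be presented as a primary success without departing from the text. Because the documents also disagree on which population is primary, the choice could be made after the data are seen. What is at stake is whether a positive finding from this trial can be read as confirmatory.

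**Working it through.** **Step 1. Is an alpha split hidden in the sample size?** Inputs from the Synopsis and section 11.1.1: hazard ratio (HR) 1.5, 80% power, 2-sided 5%, 1:1 allocation, 60% event rate, 5% dropout.

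Freedman: D = (z₁₋α/₂ + z₁₋β)² × ((HR+1)/(HR−1))² = (1.960 + 0.842)² × (2.5/0.5)² = 7.849 × 25 = 196.2. Rounded up this is 197 in total, or 98.5 per arm; the table has 99 per arm. Then N = 99/0.60/0.95 = 173.7 per arm, against 173 stated. The formula also matches the other table rows: 141.5, 74, 58.5, 48.5, 41 and 35.5 per arm, against 142, 75, 59, 49, 41 and 36.

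With half the alpha, D = (2.241 + 0.842)² × 25 = 237.6, rounded up to 238. That is 119 per arm, and 119/0.60/0.95 = 208.8, about 209 participants per arm. The plan has 173, so the full 5% is spent on one test.

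**Step 2. Chance of at least one false rejection.** Let ρ be the correlation between the two endpoint statistics and w the high-risk share of the information. The overall statistic is √w·Z(high) + √(1−w)·Z(low), with the cohorts taken as independent. The documents give neither ρ nor w, so I assume ρ from 0 to 0.9 and w from 0.5 to 0.9. Interim bounds are taken to hold each test at 5%. Apart from the closed forms shown below the table, the figures come from simulation with 1 million draws per setting.

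| Tests that count | ρ = 0 | ρ = 0.5 | ρ = 0.9 |
|---|---|---|---|
| Two overall | 9.75% | 9.1% | 7.0% |
| Three (section 11.2 row) | 14.3% | 13.6% | 11.7% |
| All six, w = 0.5 | 21.7% | 20.2% | 15.8% |
| All six, w = 0.9 | 20.5% | 19.1% | 14.9% |
| Both overall tests must succeed | 0.25% | 0.9% | 3.0% |

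- Two tests at ρ = 0: 1 − 0.95² = 9.75%.
- Three tests: the low-risk virologic test is independent of the two high-risk tests, so the chance is 1 − 0.95 × (1 − P₂), where P₂ is the two-test figure. At ρ = 0.9 this is 1 − 0.95 × 0.9296 = 11.7%.
- Treating all six as independent gives 1 − 0.95⁶ = 26.5%. That is too high, because the overall test contains the cohort tests.

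Counting only false claims of benefit, the two overall tests give about 3.5–5% and all six about 8–11%, against 2.5%.

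**Step 3. Power under the possible fixes.** Schoenfeld, assuming an O'Brien-Fleming inflation of 1.03: power = Φ(√(D/(4 × 1.03)) × ln 1.5 − z). With 99 events per arm (D = 198), √(198/4.12) × 0.4055 = 2.811.
- At 2-sided 5%: Φ(2.811 − 1.960) = Φ(0.851) = 80.3%.
- At 2-sided 2.5%: Φ(2.811 − 2.241) ≈ 71.5%, about 72%.

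These figures depend on 99 being per arm, as in the table. The text of section 11.1.1 says instead that "the trial is designed to achieve 99 events per pairwise comparison for the symptom resolution endpoints". With 99 events in total and no inflation, power is Φ(√(99/4) × 0.4055 − 1.960) = Φ(0.057), about 52%.

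**The case against.** **No familywise 5% is promised.** A reader might infer that the plan breaches its own stated error rate. The documents do not support that. The Synopsis gives 5% for a pairwise comparison, and section 5.1 ties 5% to interim bounds. The accurate statement is that multiplicity across endpoints and populations is not addressed.

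**The SAP default.** A reader might also infer that the SAP fixes 0.05 for each of the six tests. It does not, because it is written for the first three arms and has symptom resolution as secondary. Section 11.3 calls itself a brief summary and defers detail to a SAP finalized before database lock. No such SAP for lopinavir-ritonavir is among the documents reviewed, so the gap could still be closed there.

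**Co-primary may mean that both must succeed.** Error would then be about 0.3–3%, with no inflation. The word carries no decision rule, however, and sections 11.1.1 and 11.1.2 size each endpoint separately without a joint power figure. If that is the intent, it needs to be written down.

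**Six tests is the widest reading.** Section 11.3.2 uses the same overall-and-by-cohort phrasing for secondary endpoints, which suggests a reporting breakdown, and section 5.2 counts 173 per arm across both risk groups. This has force, so the six-test figure is an upper case. Against it, section 11.3.1 places the cohorts under primary analyses and the Synopsis claims power in each.

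**Conclusion.** The gap is real and moderate in size. The protocol has two primary endpoints at full alpha, up to three populations each, and no hierarchy, split or success rule; its own sections disagree on the primary population. The chance of at least one false 2-sided rejection is about 7–10%, 12–14% or 15–22%, according to whether two, three or six tests count. This rests on three assumptions: one success is enough for a claim, endpoint correlation lies between 0 and 0.9, and the high-risk share of information lies between one half and nine tenths. The documents confirm none of them. Nor do they establish that the trial's error rate is 22%, or that it violates a stated familywise limit.

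**What to change.** In protocol section 11.3.1, and in the SAP for the lopinavir-ritonavir comparison:

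1. Name the two overall ITT comparisons as the confirmatory family, controlled at 2-sided 5%. One option is a fixed sequence with symptom resolution first, since section 11.1 says that endpoint drives the study size. The other is Hochberg, if a stand-alone clearance claim is wanted.
2. Report high-risk and low-risk results as estimates with confidence intervals, without a significance claim.
3. Reconcile with this the Synopsis sentence on power in each risk population and the modified ITT row in section 11.2. Section 11.1.2 shows no calculation for either cohort alone.
4. Correct section 11.1.1 so that the text and the table agree on whether 99 events is per arm or per comparison.

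**Cost.** The wording is about one paragraph in each document. Fixed sequence leaves the 80% power for symptom resolution at 173 per arm unchanged, but allows no clearance claim if symptom resolution fails. Under Hochberg, an endpoint that must pass at 2.5% because the other misses 5% has about 72% power at a hazard ratio of 1.5 with 99 events per arm. Either way, the trial gives up a confirmatory virologic claim within a risk cohort.
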